8 TREATMENT

Eligible subjects will be randomized (6:1) to a single 4 mL Ampion intra-articular injection or a single 4 mL saline injection into the study knee.

Subjects will be randomized to an assigned subject number after confirmation of eligibility, just prior to treatment.

8.1 DOSING AND ADMINISTRATION OF STUDY MEDICATION

Appropriately trained site personnel should administer the study treatment.

If both knees are osteoarthritic, then at Screening the Investigator should select the knee that best satisfies the requirements for the study (see inclusion criteria 6 - 7) as the study knee. At the time of dose administration, the study knee should be treated with received investigational product in accordance with the randomization schedule. The other knee should receive standard of care.

Aspiration of the study knee should only occur if an effusion is present. Aspiration and volume of aspiration should be noted on the study source notes/eCRF. The study treatment should be administered as an injection into the knee joint space under sterile prep conditions, (i.e. prior to injection, the knee should be cleaned with an antiseptic).

The recommended procedure is to administer the injection into the knee joint space with the subject in the seated position with the treatment knee flexed at 90°. The area of injection is inferior lateral to the patella; lateral level of the joint line.

The Principal Investigator may determine whether anesthesia of the treatment area with a topical anesthesia or nothing is appropriate. Injection of lidocaine prior to the Ampion injection is not allowed.

The needle should be passed through the fat pad to the firm surface of the intercondylar notch. Following the withdrawal of the needle, it is recommended that fingertip pressure be applied to the injection site, and then a sterile dressing (BandAid) is used to cover the injection site. Injection should proceed easily.

The recommended needle for this injection is a 25-gauge needle that is 1.5 inches long.

Failure to easily inject should be documented as a potential non-inter-articular injection. The injector and date of administration should be recorded in the study source notes/eCRF.

Subjects should be advised to abstain from submersing their knee in water for at least 24 hours (swimming pool, baths, lakes, ect.). Showering is acceptable.

8.2 DRUG STORAGE AND ACCOUNTABILITY

Study drug should be stored at room temperature (59° – 77°F or 15° – 25°C) in a secure area with restricted access and temperature monitoring. A temperature monitor calibration must be provided to the CRO prior to receiving study drug.

The Investigator, the clinical site staff, or other personnel authorized to store and dispense investigational product is responsible for ensuring that the investigational product used in the clinical study is securely maintained as specified by the Sponsor and in accordance with the applicable regulatory requirements.

All investigational product is to be dispensed in accordance with the Investigator's prescription and it is the Investigator's responsibility to ensure that an accurate record is maintained of investigational product issued and returned.

If any quality issue is noticed upon the receipt or use of an investigational product (i.e. deficiencies in condition, packaging, appearance, associated documentation, labeling, expiry date, temperature, etc.), Ampio Pharmaceuticals, Inc. must be promptly notified. Temperature monitors, and instructions to download the temperature data to Ampio Pharmaceuticals, Inc., will be included with each site shipment of study drug.

Under no circumstances may the Investigator supply investigational product to a third party, allow the investigational product to be used other than as directed by this clinical study protocol, or dispose of investigational product in any other manner.

All investigational product, used or unused during the study, must be retained in the study kit until notification from Ampio or designated representative. Ampio, or designated representative will instruct sites on study drug returns and/or destruction of study drug.

8.3 TREATMENT COMPLIANCE

The injection of study drug will be performed by the Investigator or a designated member of the site clinical staff. A 5mL syringe, a 25-gauge needle, and a bottle of rescue medication will be included in every subject kit.

During monitoring visits, monitors will visually inspect each vial to ensure full injection volume was used. Compliance with treatment is thus assured.

9 ADVERSE EVENTS

9.1 DEFINITION OF AN ADVERSE EVENT

An adverse event (AE) is defined as any undesired medical occurrence in a subject or clinical investigation subject receiving a pharmaceutical product and which does not necessarily have a causal relationship with this treatment. An AE can therefore be any unfavorable sign and unintended sign (including an abnormal laboratory finding), symptom, or disease temporarily associated with the use of a study drug, whether or not related to the study drug.

Assessment of severity of an AE will be rated according to categories listed in TABLE 9.1.

TABLE 9.1 DEFINITIONS OF AE SEVERITY

Grade 1 (MILD): The symptom is barely noticeable to the study subject and does not influence performance or functioning. Concomitant medication is not ordinarily indicated for relief of mild AEs.
Grade 2 (MODERATE): The symptom is of sufficient severity to make the study subject uncomfortable and to influence performance of daily activities. Concomitant medication may be indicated for relief of moderate AEs.
Grade 3 (SEVERE): The symptom causes severe discomfort, sometimes of such severity that the study subject cannot continue in the study. Daily activities are significantly impaired or prevented by the symptom. Concomitant medication may be indicated for relief of severe AEs.

Determination of the relationship between the AE and the study drug will be made using the guidelines presented in TABLE 9.2.

TABLE 9.2 GUIDELINES FOR DETERMINING THE RELATIONSHIP (IF ANY) BETWEEN ADVERSE EVENT AND THE STUDY DRUG

Unrelated	The adverse event is unlikely to have been caused by study drug.
Possibly related	It is unclear whether the adverse event may have been caused by study drug.
Related	The adverse event is likely to have been caused by study drug.

9.2 DEFINITION OF A SERIOUS ADVERSE EVENT

A Serious Adverse Event (SAE) is any untoward medical occurrence that occurs at any dose that:

- Results in death
- Is life-threatening (subject is at immediate risk of death from the event as it occurred)
- Requires in-patient hospitalization (formal admission to a hospital for medical reasons) or prolongation of existing hospitalization
- Results in persistent or significant disability/incapacity
- Results in a congenital anomaly/birth defect

Important medical events that may not result in death, are not life-threatening, or do not require hospitalization may be considered SAEs when, based on appropriate medical judgment, they may jeopardize the subject and may require medical or surgical intervention to prevent one of the outcomes listed in this definition. Examples of such events include allergic bronchospasm requiring intensive treatment in an emergency room or at home, blood dyscrasias or convulsions that do not result in in-patient hospitalization, or the development of drug dependency or drug abuse.

Hospitalizations for elective surgery or other medical procedures that are not related to a treatment-emergent AE are not considered SAEs.

9.3 RECORDING OF ADVERSE EVENTS AND SERIOUS ADVERSE EVENTS

Recording and reporting of adverse events should be in accordance with the FDA final “Guidance for Industry and Investigators Safety Reporting Requirements for INDs and BA/BE Studies” of December 2012.

Any AE is to be recorded in the eCRF. In order to avoid vague, ambiguous, or colloquial expressions, the AE should be recorded in standard medical terminology rather than the subject’s own words. Whenever possible, the investigator should combine signs and symptoms that constitute a single diagnosis.

The existence of an AE may be concluded from a spontaneous report of the subject; from the physical examination; or from special tests e.g., laboratory assessments, where applicable, or other study-specified tests (source of AE).

The reporting period begins from the time that the subject receives IA injection at the Baseline visit through subject’s Final Visit at 12 weeks. Any events continuing at study exit will be followed for 30 days or to resolution, or until no improvement is expected, whichever comes first. Any SAE occurring after the reporting period must be promptly reported if a causal relationship to the investigational drug is suspected. If the subject begins a new therapy, the safety reporting period ends at the time the new treatment is started, however, death must always be reported when it occurs during the 12-week study period, irrespective of intervening treatment.

Each AE is to be evaluated for duration, severity, seriousness, and causal relationship to the investigational drug. The action taken and the outcome must also be recorded.

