3 STUDY DESIGN

3.1 STUDY DESIGN OVERVIEW

A confirmatory, randomized, phase 3 study with a 7-day screening period for each subject followed by a 12-week participation period. A total of 171 subjects with knee pain and decreased function due to severe osteoarthritis (KL 4) will be enrolled in a 6:1 randomization schema: 4 mL Ampion intra-articular injection: 4 mL saline intra-articular injection. Study visits will include: Screening visit, Baseline, a 24-hour, a post-injection follow-up phone call, Week 2 phone visit, Week 6, Week 10 phone visit, and Week 12 for a total of 7 visits. Screening, Baseline, Week 6 and Week 12 are in-office visits.

The clinical effects of Ampion treatment on OA pain will be evaluated during in-clinic visits at 6 and 12 weeks, and telephone contacts at 2 and 10 weeks, using the Western Ontario and McMaster Universities Arthritis Index (WOMAC®) and the Patient's Global Assessment of disease severity (PGA).

The WOMAC® is a validated Osteoarthritis scoring system and sets the standard for the subject response. In order not to bias the collection of data, only questions from the validated WOMAC scale and PGA will be asked of subjects.

Clinical benefit will be established by evaluation of the OMERACT-OARSI response using the WOMAC and PGA scales as assessed during the in-office visits and phone visits. Safety will be assessed by recording adverse events (post-injection and at all follow-up contacts), physical examinations, vitals (Baseline, Weeks 6 and 12), and laboratory analysis (Screening and Week 12).

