9.3.1 AE Follow up

All AEs occurring during the study are to be followed up in accordance with good medical practice until they are resolved, stabilized or judged no longer clinically significant or, if a chronic condition, until fully characterized. Any AEs that are considered drug-related (possibly related, definitely related) must be followed for 30 days, or to resolution, or until no improvement is expected, whichever occurs first.

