10.3.11 Data presentation**10.3.11.1 Demographic and Baseline Characteristics:**

Demographic (e.g., age, sex, race, and ethnicity) and Baseline characteristics (e.g., weight, height, prior injection of another intra-articular therapeutic for OA of the knee) summarized using descriptive statistics, overall and by treatment group for the ITT analysis population.

10.3.11.2 Medical History and Physical Examination:

The number and percent of subjects with past and current medical disorders at the time of randomization will be presented overall for the ITT analysis population. Results of any abnormalities documented from the abbreviated physical examination at Baseline and Week 12, will be summarized overall for the safety and ITT analysis populations.

10.3.11.3 Concomitant Medications or Treatments:

The number and percent of subjects receiving concomitant medications or treatments prior to and during the study and at the final visit will be tabulated and presented overall for the ITT

analysis population. Concomitant medications/treatments will be summarized using descriptive statistics and will be presented by type of drug (WHO DRUG classification) overall for the safety and ITT analysis populations.

10.3.11.4 Safety data:

Safety data will be evaluated by changes in vital sign measurements, physical exam, laboratory analysis, and the frequency and severity of AEs. Concomitant medication will be recorded for safety.

Adverse events:

The Investigator is responsible for monitoring the safety of subjects who have enrolled in the study. All AEs considered related, or possibly related to Ampion™, will be followed until the event resolves or stabilized without further change. Subjects will be followed for the occurrence of AEs until 12 weeks after the first dose of study medication.

Investigators are required to document all AEs occurring during the clinical trial, commencing with the first day of treatment through the end of study. AEs should be properly documented on the appropriate CRF pages.

The severity of AEs (mild, moderate, severe), relatedness (related, possibly related, unrelated) along with the duration, action taken, and outcome (e.g., study withdrawal) will also be recorded. In addition, events meeting the criteria of a Serious Adverse Event (SAE) must be reported to the Sponsor within 24 hours on the SAE reporting forms.

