4.9 Data presentation

4.9.1 Demographic and Baseline Characteristics:

Demographic (e.g., age, sex, race, and ethnicity) and Baseline characteristics (e.g., weight, height, prior injection of another intra-articular therapeutic for OA of the knee) will be summarized using descriptive statistics, overall and by treatment group for the ITT analysis population. Demographic data for the historic control will be provided and summarized.

4.9.2 Medical History and Physical Examination:

The number and percent of subjects with past and current medical disorders at the time of randomization will be presented overall for the ITT analysis population. Results of any abnormalities documented from the abbreviated physical examination at Baseline and Week 12, will be summarized overall for the safety and ITT analysis populations.

4.9.3 Concomitant Medications or Treatments:

The number and percent of subjects receiving concomitant medications or treatments prior to and during the study and at the final visit will be tabulated and presented overall for the ITT analysis population. Concomitant medications/treatments will be summarized using descriptive statistics and will be presented by type of drug (WHO DRUG classification) overall for the safety and ITT analysis populations. Concomitant medication and treatment data for the historic control will be provided and summarized.

4.9.4 Safety data:

Safety data will be evaluated by changes in vital sign measurements, physical exam, laboratory analysis, and the frequency and severity of AEs. Concomitant medication will be recorded for safety.

Adverse events:

The Investigator is responsible for monitoring the safety of subjects who have enrolled in the study. All AEs considered related, or possibly related to Ampion™, will be followed until the event resolves or stabilizes without further change. Subjects will be followed for the occurrence of AEs until 12 weeks after the first dose of study medication.

Investigators are required to document all AEs occurring during the clinical trial, commencing with the first day of treatment through the end of study. AEs should be properly documented on the appropriate CRF pages.

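### Protocol 9.3 ends safety reporting inside the 12 weeks when an undefined new therapy starts, in conflict with Protocol 10.3.11.4, SAP 4.9.4 and the visit schedules

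*Protocol*

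**What the plan says.** Protocol 9.3 opens the reporting period at the intra-articular injection and closes it at the 12-week Final Visit. It then adds: "If the subject begins a new therapy, the safety reporting period ends at the time the new treatment is started". One exception follows in the same sentence: "death must always be reported when it occurs during the 12-week study period, irrespective of intervening treatment". For events outside the period, 9.3 says: "Any SAE occurring after the reporting period must be promptly reported if a causal relationship to the investigational drug is suspected".

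Other sections give a longer window.

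- Protocol 10.3.11.4, repeated in SAP 4.9.4: "Subjects will be followed for the occurrence of AEs until 12 weeks after the first dose of study medication".
- SAP 4.9.4, repeated in Protocol 10.3.11.4: "Investigators are required to document all AEs occurring during the clinical trial, commencing with the first day of treatment through the end of study".
- Protocol 5.1.3 to 5.1.7, Protocol Table 6.1 and the SAP section 10 schedule call for AE recording at each post-dose contact (Day 1 and Weeks 2, 6, 10 and 12). Both schedules and Protocol 5.1.8 also call for it at Early Termination.

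SAP 5.2 counts an AE as treatment-emergent if it starts or worsens after the initial dose. It sets no end linked to another therapy. The Safety population (Protocol 10.3.1) is everyone who received study medication.

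**The concern.** The two sets of instructions cannot both be followed for a subject who starts another therapy before Week 12. One site may stop collecting AEs for that subject. Another may carry on as the visit instructions require. The trigger is also left to the reader: the plan supplies rescue acetaminophen (Protocol 5.1.11), expects standard of care for the other knee (Protocol 8.1), and tabulates medication started on study (SAP Tables 14.3.10.2 and 14.3.10.5). Nothing says whether any of these counts as a new therapy.

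Safety is the stated secondary objective (Protocol 3.2.2, SAP 2.2). If collection stops early for some subjects while the tables still divide by all treated subjects, the reported incidence rests on unequal observation that no passage acknowledges. The Safety Monitoring Committee, which is to review any serious AE (Protocol 3.3), would also depend on which reading a site adopts.

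**Working it through.** The point rests on a comparison of text. The plan gives no figure to reproduce.

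**Step 1. Does the cut operate inside the 12 weeks?** If the clause governed only follow-up after study exit, an exception for deaths during the 12-week period would have no purpose, since those deaths would already fall in an open period. The exception makes sense only if a new therapy can close the period before Week 12.

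**Step 2. What falls outside mandatory reporting after the cut, reading 9.3 alone?**

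| Event with onset after the new therapy, within 12 weeks | Still required by 9.3? |
|---|---|
| Death | Yes, by the exception |
| Non-fatal serious AE, drug relation suspected | Yes, by the rule for events after the period |
| Non-fatal serious AE, drug relation not suspected | No |
| Non-serious AE | No |

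**Step 3. What do the other passages require for the last two rows?** Protocol 10.3.11.4 and SAP 4.9.4 require both to be documented through the end of study. The visit instructions and schedules require AEs to be recorded at every remaining contact. None has an exception for new therapy. Protocol 9.4.1, which asks for all serious AEs within 24 hours, also points this way for the third row. It is a secondary conflict, because it can be read as setting entry timing within the 9.3 period.

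**Step 4. Does the subject leave the denominator?** Starting a therapy does not in itself remove anyone. Protocol 7.2 says a protocol violation does not cause withdrawal unless it puts the subject at significant risk, and the Safety population is all treated subjects. SAP Tables 14.3.1 and 14.3.2 name that population; Tables 14.3.3 to 14.3.6 name none.

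**Step 5. Direction.** Crude incidence = (subjects with at least one recorded treatment-emergent AE) / (all treated subjects). The cut can remove events from the numerator and leaves the denominator unchanged. Incidence under the cut is therefore no higher than under full collection. It is equal if each affected subject already has a recorded event of that type or has none after the cut.

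**Step 6. Size.** Let f be the share of subjects who start a new therapy and t the day they start. Against a nominal 84-day period, the share of observation time outside mandatory reporting is f × (84 − t)/84. The documents give neither f nor t, so these values are assumptions:

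- f = 5%, t = 70: 0.05 × 14/84 = 0.8%
- f = 5%, t = 42: 0.05 × 42/84 = 2.5%
- f = 40%, t = 42: 0.40 × 42/84 = 20%
- f = 40%, t = 14: 0.40 × 70/84 = 33%

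The spread from 0.8% to 33% shows that the documents do not fix the size. It describes observation time, not a proportion of AEs lost.

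**The case against.** The strongest defence is that the clause limits reporting and not recording. It speaks of a reporting period, and the text around it deals with serious AEs and deaths, whereas 10.3.11.4 and SAP 4.9.4 speak of documenting AEs. On that reading AE collection continues. This is a possible reading and a reason not to claim that data will be lost. It does not settle the matter: 9.3 covers the recording of all AEs and defines only one period, and a site could reasonably apply the clause to all of them.

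A second defence is that the specific rule overrides the general one. Then 10.3.11.4, SAP 4.9.4 and the schedules misstate the collection window and would need amending instead. Reconciliation is needed either way.

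Third, the trigger may be rare. Protocol 5.1.11 prohibits many new osteoarthritis treatments, exclusion 11 keeps out subjects whose osteoarthritis treatment is likely to change, and 7.2 lets the investigator withdraw a subject. All of this stands and limits the likely impact.

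Two stronger readings are tempting. A reader might infer that 9.3 contradicts its own sentence "Any AE is to be recorded in the eCRF", or 9.3.1: "All AEs occurring during the study are to be followed up in accordance with good medical practice". Both are weak support. The first says what to record, and the section then sets the period; the second concerns follow-up of events that have occurred. A reader might also infer that the later safety contacts are cancelled. No passage cancels a contact, and the next one is still needed to collect events that began before the cut.

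**Conclusion.** The conflict is real and should be resolved. Protocol 9.3 closes the safety period inside the 12 weeks on an undefined trigger, and Protocol 10.3.11.4, SAP 4.9.4 and the visit schedules do not. Where a site applies the clause to AE collection, non-serious AEs and non-fatal serious AEs not suspected to be related can go unrecorded in subjects who remain in the denominator, and crude treatment-emergent AE incidence can only fall or stay the same.

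The direction assumes that at least some sites read the clause as ending collection. The size cannot be derived. A reader might infer that the safety comparison is tilted towards Ampion; the documents do not support that, because nothing indicates which arm would start new therapy more often or earlier. Nor do they support a claim that deaths or suspected drug-related serious AEs would be missed, since 9.3 keeps both reportable. The primary endpoint, sample size and efficacy tests are unaffected.

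**What to change.** In Protocol 9.3, delete the new-therapy cut for AEs and serious AEs. State one collection period, from injection to end of study as SAP 5.2 defines it (the Week 12 visit with its window, unless terminated early), whatever other therapy is started. AEs also continue to be recorded at the Early Termination visit (Protocol 5.1.8). Keep the requirement that death is always reported. Protocol 10.3.11.4 and SAP 4.9.4 can then stand as written, and the tension with 9.4.1 goes.

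Optionally, flag AEs with onset after a medication started on study, using the start dates that Protocol 5.1.11 already requires, and read the result alongside planned Tables 14.3.10.2 and 14.3.10.5.

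The cost is one clause in a protocol amendment. No visits or AE questions are added, since they are already scheduled. The downside is that reported AE rates may be slightly less favourable and may include events caused by the other therapy, which the optional flag would help to show.
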